### 8.1.2 Primary Endpoint Supportive Analyses

The primary endpoint will also be analyzed using the same method in the as-treated population.

The following viremia descriptively summarized by treatment arm, with comparison method indicated in parentheses:

- Change from baseline in log10 viral load by scheduled time point (Kruskal-Wallis). Along with the Kruskal-Wallis test, a one-way ANOVA will be used to compare treatment effect separately at each time point.
- Proportion of measurements above the lower limit of quantification (Fisher exact)

All viremia data will be listed and individual profiles of viremia over time will be presented for each subject. Viremia levels below the lower limit of quantification will be considered as 0 in the log10 viral load summaries and indicated as BLQ in the listings.

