#### 4. General Statistical Considerations

All statistical analyses will be conducted using statistical analysis system SAS® Version 9.4 or higher (SAS Institute, Cary, NC).

Analysis of the data from this study will be descriptive in nature. Confidence intervals and p-values will be descriptive due to small sample size in this study. N, mean, standard deviation, median, minimum and maximum, and 95% CI will be used for continuous data and number and percentage

will be used for categorical/count data, unless specified otherwise. No analysis will be performed until the data are unblinded.

All tables, listings, and figures will be presented by assigned treatment. The treatments below will be used for presentations:

- AT-752 750 mg TID
- AT-752 up to 1000 mg BID or TID
- AT-752 up to 1500 mg BID
- Placebo (pooled Cohort 1 through Cohort 3)

All data listings will be sorted by treatment and subject number. If a regimen is repeated in more than one cohort, the matching cohorts will be pooled as one treatment.

Unless otherwise specified, no algorithm for imputation of missing data will be employed.

Study days are calculated with respect to the first date of study drug exposure (First Dose Date) as below:

- If the assessment/observation date is on or after the first dose date, then  
Study Day = Assessment/Observation Date – First Dose Date + 1;
- Otherwise, Study Day = Assessment/Observation Date – First Dose Date

Baseline will be defined as the last non-missing assessment (including repeated and unscheduled assessments) before administration of the first dose of study drug, unless otherwise specified.

For summary of safety assessments, if there are repeated measurements at a time point, the first non-missing assessment at that time point will be used in the summary tables.

Unscheduled results will not be included in the summary tables, except for determining baseline, but will be presented in data listings.

The methodology and data handling specifications for PK data are detailed in Section 11.

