#### **4.3. Analysis Population**

Primary endpoint analyses will be applied to the modified intent-to-treat population (mITT), which is defined as all randomized subjects who received at least 1 dose (full dose, unless assigned to placebo) of study drug (AT-752 or matching placebo) and have baseline and at least one post-baseline virology measurement. Change from baseline viral load (DENV RNA) will be compared between each AT-752 arm and a combined placebo group.

As-treated population is defined as all subjects who received at least 1 dose (full dose, unless assigned to placebo) of study drug (AT-752 or matching placebo) based on the actual treatment the patients received and had baseline and at least one post-baseline virology measurement.

The safety population will include all subjects who receive at least 1 dose of study drug.

The PK population will include all subjects who receive at least 1 dose of AT-752 and have sufficient concentration data to support accurate estimation of at least 1 PK parameter. PK parameter summaries will include only subjects in the PK population who have sufficient concentration measurement data to support estimation of the parameter. All subjects excluded from the PK population will be documented in the data listings.

The PD population will be the mITT population, which includes subjects who received at least 1 dose (full dose, unless assigned to placebo) of study drug and have baseline and at least 1 post-baseline viral load measurement.

The Per Protocol (PP) population will include the subset of the modified intent-to-treat population who completed study drug treatment without a major protocol violation that impact patient safety or data quality.

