### **8.1 Primary Efficacy**

#### **8.1.1 Primary Endpoint**

The primary objective of this study is to evaluate the antiviral activity of AT-752 compared with placebo on change from baseline in DENV viral load (DENV RNA as measured by RT-qPCR) based on the log-10 scale at specified time points:

$$y_i = v_i - v_0$$

where  $v_i$  is the log10 DENV viral load measured at timepoint  $t_i$  and  $v_0$  is the log10 DENV viral load measured at baseline. Viral load measurements that are below the lower limit of quantification (LLOQ) will be set to  $0.5 \times \text{LLOQ}$  in the analysis.

Change from baseline in DENV viral load ( $y_i$ ) will be analyzed with repeated measures mixed model using the method of restricted maximum likelihood (REML). The model will include baseline viral load, treatment, time, and treatment-by-time interaction as fixed factors. An unstructured covariance matrix will be specified for the repeated statement. In case a mixed model with unstructured (UN) covariance matrix fails to converge, a compound symmetry (CS) structure will be used as an alternative. If neither of these converges, independent (ID) structure will be used. If none of these converges, the change from baseline by scheduled time point (ANOVA, Kruskal-Wallis) analysis will be presented as the primary analysis. The treatment group least squares mean (LSM) estimates for mean change from baseline and treatment group differences at each time point, with 80% CI, 95% CI and p-value will be presented.

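### The by-visit ANOVA and Kruskal-Wallis tests in SAP 8.1.2, also the last fallback in 8.1.1, carry no baseline covariate and no stated arm-versus-pooled-placebo contrast

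*SAP*

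**What the plan says.** SAP 4.3 fixes the comparison: "Change from baseline viral load (DENV RNA) will be compared between each AT-752 arm and a combined placebo group". Protocol 8.3.1 says the same. SAP 4 lists four groups for presentation, three AT-752 regimens and one placebo group pooled over the cohorts, and merges cohorts if a regimen is repeated.

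For the main model, SAP 8.1.1 states: "The model will include baseline viral load, treatment, time, and treatment-by-time interaction as fixed factors". The outcome is log10 viral load at the time point minus a term that "is the log10 DENV viral load measured at baseline".

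SAP 8.1.2 then lists a Kruskal-Wallis test on change from baseline at each scheduled time point and adds: "Along with the Kruskal-Wallis test, a one-way ANOVA will be used to compare treatment effect separately at each time point". It gives no covariate, pairwise contrast or significance level for either test.

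The same pair ends the fallback sequence in SAP 8.1.1. After unstructured and compound symmetry: "If neither of these converges, independent (ID) structure will be used". Then: "If none of these converges, the change from baseline by scheduled time point (ANOVA, Kruskal-Wallis) analysis will be presented as the primary analysis".

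**The concern.** A one-way ANOVA F test and a Kruskal-Wallis test ask whether any of the groups differ. The p-value names no arm and has no direction. It can be small because two AT-752 doses differ from each other, or because one dose does worse than placebo. That is not the question in SAP 4.3, so agreement or disagreement with the mixed model is hard to interpret.

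The outcome is also unadjusted change. Subtracting baseline does not remove chance baseline imbalance when change is correlated with baseline. With about 15 subjects per group, such imbalance can be a visible fraction of the 0.5 log10 observed effect that SAP 4.1 calls suggestive of a signal.

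Apart from the Fisher exact test on quantifiable measurements, these are the only analyses listed in SAP 8.1.2 that use a method other than the mixed model. They are the natural check on it, and the check should target the same comparison.

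**Working it through.** **Inputs from SAP 4.1 and 3.1.** Effect 1 log10, SD 1.25, 15 subjects per AT-752 arm, 15 pooled placebo (3 cohorts × 5), one-sided level 0.10 at one time point. The SAP sets no level for the 8.1.2 tests, so several are shown.

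**1. The plan's own figures.** The standard error of a 15-versus-15 difference is 1.25 × √(2/15) = 0.456, so the noncentrality is 1/0.456 = 2.19. The noncentral t with 28 df gives 0.810 (plan: 80%). For 15 versus 5 it gives 0.592 (plan: 59%). Both reproduce. They belong to a one-sided two-group contrast, not to an omnibus test.

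**2. Power of the omnibus F, four groups of 15.** λ = n × Σ(μ − mean)² / SD², with 3 and 56 df. If all three doses have a 1 log10 effect, the means are 0, 1, 1, 1 and Σ = 0.75, so λ = 15 × 0.75 / 1.5625 = 7.2. One active dose gives the same λ. The single-arm contrast uses 56 df and noncentrality 2.19.

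| Two-sided level | Omnibus F | One arm vs pooled placebo, unadjusted |
|---|---|---|
| 0.05 | 0.570 | 0.577 |
| 0.10 | 0.695 | 0.698 |
| 0.20 | 0.818 | 0.814 |

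The two are practically equal in these scenarios. Kruskal-Wallis, from 20,000 simulated normal trials with all three doses active, gives 0.53, 0.67 and 0.80.

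**3. Direction.** If one dose is 1 log10 worse than the other three groups, Σ and λ are unchanged. The omnibus F then rejects with the same probability, 0.695 at level 0.10.

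**4. Baseline adjustment.** Let r be the size of the correlation between change and baseline. The documents give no value; 0.3 to 0.7 is assumed. ANCOVA multiplies residual variance by 1 − r². Power is for the single-arm contrast, one-sided 0.10, with 55 df; without the covariate (56 df) it is 81.4%. The shift is what a 1-SE chance baseline imbalance adds to the unadjusted difference: slope × SD of baseline × √(2/15). Since slope × SD of baseline = r × SD of change, this equals r × 1.25 × √(2/15), and no baseline SD is needed.

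| r | Variance cut | Residual SD | Power | Shift (log10) |
|---|---|---|---|---|
| 0.3 | 9% | 1.192 | 84.1% | 0.14 |
| 0.5 | 25% | 1.083 | 89.1% | 0.23 |
| 0.7 | 51% | 0.893 | 96.1% | 0.32 |

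**The case against.** Several points on the other side stand.

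- **Descriptive status.** SAP 4 calls confidence intervals and p-values descriptive, and SAP 4.1 rests interpretation on the totality of the data. No decision rule uses these tests.
- **Other analyses.** The baseline-adjusted mixed model is repeated in the as-treated (SAP 8.1.2) and per-protocol (SAP 8) populations, and SAP 10 adds multiple imputation under a missingness trigger. These address arm-versus-placebo differences.
- **The fallback is remote.** The independent structure is an ordinary linear model and should practically always fit, so the final step in 8.1.1 is unlikely to be used. The tests in 8.1.2 are run regardless.
- **A global unadjusted test is a legitimate companion** to an adjusted model. The omnibus reading is itself inferred from the test names and the group list, and there may be fewer than four groups.

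Three stronger readings are tempting, and the documents do not support them.

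- A reader might infer that these analyses yield no arm-versus-placebo information. But 8.1.2 promises summaries by arm, and the last sentence of 8.1.1, placed after the fallback, promises least squares mean differences with intervals. That sentence can be read to cover ANOVA. The wording is unclear rather than plainly lacking, although Kruskal-Wallis supplies no such estimate.
- A reader might infer that baseline is discarded. It is subtracted in the outcome; only the covariate is missing.
- A reader might infer a large power loss by setting 0.695 against 0.843 at level 0.10. The higher figure is for all doses combined, 45 versus 15 (noncentrality 2.68), a contrast the SAP does not plan.

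**Conclusion.** The point holds as one of specification, with modest impact. As named, the two by-visit tests do not address the comparison in SAP 4.3, and they omit the covariate that the primary model uses. At the same two-sided level there is essentially no power cost against an unadjusted single-arm contrast (0.695 against 0.698).

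The benefit of a change is twofold: a result with a direction for each arm, and baseline adjustment. The second is worth a 9% to 51% cut in residual variance, about 3 to 15 percentage points of one-sided power, and removal of a 0.14 to 0.32 log10 shift per 1-SE imbalance. Those figures rest on the assumed correlation of 0.3 to 0.7, SD 1.25 and 15 per group. A larger shift needs a stronger correlation: for example, slope −0.7 with baseline SD 1.5 gives 0.38 log10 but implies r = 0.7 × 1.5 / 1.25 = 0.84.

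**What to change.** In SAP 8.1.2, replace the one-way ANOVA with a per-visit ANCOVA of change in log10 RNA on treatment and baseline log10 RNA. Report each AT-752 arm minus pooled placebo with 80% and 95% confidence intervals, matching the intervals in 8.1.1. Pair it with a rank test of each arm against pooled placebo (Wilcoxon, or rank ANCOVA with baseline). Kruskal-Wallis may stay as an optional global test, labelled as such. In SAP 8.1.1, name this ANCOVA as the last fallback and say that the closing sentence on differences and intervals applies to it.

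The cost is SAP wording and a changed model statement. No new data, visits or subjects are needed.

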## 9. Safety Analysis

All safety summaries and analyses will be based upon the safety population. Summaries will be presented by treatment group and overall.

### 9.1 Adverse Events

An AE is defined as any untoward medical occurrence associated with the use of a drug in humans, whether or not considered drug related. The AE's relationship to study treatment will be evaluated by the investigator. The following relationships will be collected on eCRF: not related, or related. If the relationship information is missing, the AE will be considered related in the summary but will be presented as missing in the data listings.

A treatment-emergent AE (TEAE) is defined as any event not present before exposure to study drug or any event already present that worsens in intensity or frequency after exposure. The time frame for treatment emergent adverse events in this study is from the first dose through Day 28 or withdrawal from the study, whichever happens first. TEAE that are evaluated as possibly related to study drug, regardless of timing, will be considered treatment-related TEAE for summary purpose.

The severity of AEs will be classified by the investigator as Grade 1 mild, Grade 2 moderate, Grade 3 severe, Grade 4 potentially life threatening and Grade 5 death. If the severity information is missing, the AE will be considered severe in the summary but will be presented as missing in the data listings.

In all AE summaries, a subject with 2 or more events within the same level of summarization will be counted only once in that level using the most severe incident or most related incident. Percentages will be based on the number of subjects in the safety population.

An overall AE summary will be generated presenting the frequency and percentage of subjects for the following:

- Any TEAE
- Any treatment related TEAE
- Any TEAE of grade 2 or higher
- Any treatment related TEAE of grade 2 or higher
- Any TEAE of grade 3 or higher
- Any treatment related TEAE of grade 3 or higher
- Any SAE
- Any treatment related SAE
- Any treatment related AE leading to early study drug discontinuation
- Any treatment related AE leading to early study discontinuation
- Any death

All AEs will be coded using MedDRA (version 24.1 or up). The TEAEs will also be summarized by system organ class (SOC), preferred term (PT), by severity and relationship to treatment. These TEAE summary tables will be sorted by SOC and PT. System organ class will be displayed in descending order of overall frequency then alphabetically. Preferred term will be displayed in descending order of overall frequency and then alphabetically within SOC.

All AEs will be presented in a data listing. Separate data listings will be generated for treatment-related AEs, SAEs, and AEs leading to study discontinuation.

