#### 7.3.1.5 **Assessment of Causality**

The investigator's assessment of an AE's relationship to study drug is part of the documentation process.

The investigator will assess causality (i.e., whether there is a reasonable possibility that the study drug caused the event) for all AEs and SAEs. The relationship will be classified as follows:

- Not related: There is not a reasonable possibility of relationship to study drug. The AE does not follow a reasonable temporal sequence from study drug administration, or can be reasonably explained by the subject's clinical state or other factors (e.g., disease under study, concurrent diseases, and concomitant medications).
- Related: There is a reasonable possibility of relationship to study drug. The AE follows a reasonable temporal sequence from study drug administration and cannot be

reasonably explained by the subject's clinical state or other factors (e.g., disease under study, concurrent diseases, or concomitant medications), represents a known reaction to the study drug or other drugs in its class, is consistent with the known pharmacological properties of the study drug, and/or resolves with discontinuation of the study drug (and/or recurs with re-challenge, if applicable).

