### **8.3.3 Safety Analyses**

Adverse events will be coded by preferred term and system organ class using the latest version of the MedDRA. Severity of AEs will be graded according to the grading scales modified from DAIDS Table for Grading the Severity of Adult and Pediatric Adverse Events (DHHS 2017). All AE data will be presented in a data listing. Treatment-emergent AEs will be summarized by treatment and overall, as well as by severity and relationship to study drug. Serious AEs and AEs leading to discontinuation of study drug will also be presented in the data listings and summarized by treatment and overall.

Relevant laboratory, vital sign (pulse rate, respiratory rate, blood pressure, and temperature), and ECG data will be displayed by time. Where appropriate, graded laboratory abnormalities will be summarized by treatment (DHHS 2017). Shift tables will be generated to summarize baseline and post-baseline severity grades. Physical examination findings will be presented in a data listing.

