### **5. Subject Disposition**

#### **5.1 Disposition**

The following will be summarized for the full analysis set, by treatment and overall for all subjects:

- The number of subjects who completed the study drug per protocol
- The number of subjects who completed the study
- The number of subjects who did not complete the study and study drug treatment (both overall and according to reasons for discontinuation from the study and study drug treatment)
- The number of subjects in each analysis population.

Subject disposition data will be presented in a data listing.

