### 14. Changes in the Planned Analysis

There are no changes to the planned analyses described in the protocol.

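### SAP 9.1 tabulates only drug-related AEs leading to discontinuation, although Protocol 8.3.3 promises all that stop study drug; SAP 4 also keeps unscheduled results out of the worst-grade laboratory table

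*SAP*

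**What the plan says.** **AEs leading to discontinuation.** Protocol 8.3.3 states: "Serious AEs and AEs leading to discontinuation of study drug will also be presented in the data listings and summarized by treatment and overall". It sets no condition on relationship to study drug. The overview in SAP 9.1 covers discontinuation in two rows only, "Any treatment related AE leading to early study drug discontinuation" and "Any treatment related AE leading to early study discontinuation". On listings, the same section says: "Separate data listings will be generated for treatment-related AEs, SAEs, and AEs leading to study discontinuation". SAP 14 states: "There are no changes to the planned analyses described in the protocol".

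Under Protocol 7.3.1.5, the investigator may class an AE as not related when it can reasonably be put down to the subject's "clinical state or other factors (e.g., disease under study, concurrent diseases, and concomitant medications"). SAP 5.1 tabulates non-completers "according to reasons for discontinuation from the study and study drug treatment".

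**Laboratory results.** SAP 4 sets a general rule: "Unscheduled results will not be included in the summary tables, except for determining baseline, but will be presented in data listings". Where a safety time point has repeat values, the first non-missing one goes into the tables. SAP 9.2 plans a shift table from baseline to the worst DAIDS abnormality after baseline and states no exception to SAP 4.

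**Arm used for display.** SAP 4 presents every table, listing and figure by assigned treatment. In SAP 4.3, only the as-treated population, a virology set, is defined by the treatment actually received.

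**The concern.** Safety is a secondary objective, and the study is meant to support dose selection for later trials. Stopping study drug because of any AE is a direct measure of tolerability, and the protocol undertook to show it by arm. These patients are acutely ill with dengue, so many events can be attributed to the disease. Once the row is restricted to related events, comparing arms on it depends on the investigator's causality call. Because SAP 14 declares no change, the narrowing is also undeclared.

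The laboratory point is similar in kind. A table headed as the worst grade should contain the worst grade. Unscheduled samples are often drawn because something looks wrong, and those are the results the general rule leaves out.

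**Working it through.** The main point needs no model. It rests on comparing texts and on simple counts.

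**1. Overview rows.** SAP 9.1 lists 11 rows.

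| Category | All causes | Treatment-related |
|---|---|---|
| Any TEAE | yes | yes |
| Grade 2 or higher | yes | yes |
| Grade 3 or higher | yes | yes |
| SAE | yes | yes |
| Leading to study drug discontinuation | **no** | yes |
| Leading to study discontinuation | **no** | yes |
| Death | yes | not listed |

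Count: 4 × 2 + 2 + 1 = 11. Four categories are paired. The two on discontinuation are not, and one of these is the category for which the protocol promised all events.

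**2. Listings.** The dedicated listing is for leaving the study. Protocol 4.3.2 encourages subjects who stop treatment to stay in follow-up, so stopping drug and leaving the study are different events. That listing does not stand in for one on study drug. The general listing of all AEs in SAP 9.1 does keep the data.

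**3. Size.** The documents give no rate for AE-driven stops. Assume k subjects in an arm of 15 stop study drug for an AE judged not related, and none stops for a related AE. The overview row shows 0/15 = 0%. The protocol's summary would show k/15:

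- k = 1: 1/15 = 6.7%
- k = 2: 2/15 = 13.3%
- k = 3: 3/15 = 20.0%

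These counts are assumptions chosen to show scale.

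**4. Laboratory shift table.** Let S be the scheduled post-baseline grades and U the unscheduled ones. The table as written reports max(S). The worst grade is max(S ∪ U), and max(S) ≤ max(S ∪ U). Leaving out U can therefore only leave the grade equal or lower. The first-value rule differs: it understates when a repeat is worse and overstates when a repeat corrects a spurious first value.

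From the Schedule of Events (Protocol Table 3-1):

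- Chemistry, hematology and coagulation after baseline: Days 2, 4, 6, 8, 14 and 28, which is 6 draws. From Day 2 to Day 8 this covers 4 of 7 days.
- Urinalysis after baseline: Days 6 and 8, which is 2 collections.

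A result on Day 3, 5 or 7 would normally be unscheduled and so outside the table. Extra results are foreseen: the notes to Table 3-1 allow additional urinalysis when clinically indicated, and Protocol 7.3.2 allows some retests. Protocol 8.3.3 describes shift tables as summarizing grades, so they count as summary tables under SAP 4.

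**5. Assigned versus received treatment.** If a subject received the wrong treatment, the SAP 4 rule would put that subject's safety and PK summaries under the wrong arm. Nothing in the documents suggests that this is likely.

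**The case against.** The best counter-argument is that the information exists elsewhere. Protocol 8.3 promises discontinuations from study and from treatment with reasons, Protocol 4.3.1 names an intolerable AE as a reason for withdrawal without a causality test, and SAP 5.1 tabulates reasons by arm. If the recorded reasons follow that list, a count of all-cause AE stops will appear. All AEs are listed, serious or grade 3 and higher events are counted whatever their cause, and an AE with missing relationship counts as related. This stands as mitigation. However, the SAP does not give the reason categories, and SAP 5.1 uses a full analysis set that SAP 4.3 does not define. A disposition count is also not an AE summary, and only AEs actively judged not related are at issue.

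It is also fair that Protocol 8.3.3 promises nothing about AEs leading to *study* discontinuation and does not require a *separate* listing. Those two additions are for consistency; they do not repair a broken promise.

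The size is assumed. In the 65-subject Phase 1 study, all subjects completed except one who withdrew consent, with no SAEs and no AE of grade 3 or higher. Those were healthy volunteers, so this gives no rate for dengue patients, but it does not support a high one either. Protocol 1.2.1 also reports that vomiting appeared to increase with dose from 750 mg.

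On the laboratory table, a programmer could let the specific word in SAP 9.2 override the general rule in SAP 4. But SAP 4 names baseline as its only exception, and two programmers could produce different tables. All values remain listed with out-of-range flags, Protocol 7.3 requires clinically significant results to be reported as AEs, and blood tests at an early termination visit count as scheduled.

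Finally, cohort progression rests on the Safety Review Committee's unblinded review, not on this overview.

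**Conclusion.** The concern holds. The SAP does not deliver the all-cause summary of AEs leading to study drug discontinuation that Protocol 8.3.3 promises, and SAP 14 does not declare the change. This follows from the text and needs no assumption. Its numerical effect is unknown: each omitted subject is 6.7 percentage points in an arm of 15, and the range up to 20.0% rests on assumed counts.

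The laboratory point also holds as written. The shift table can understate the worst grade through the exclusion of unscheduled results, and can err either way through the first-value rule. How often cannot be estimated from the documents.

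Display by assigned treatment is minor and matters only if a misallocation occurs. No data are lost in any of the three cases, so this should be corrected but does not threaten the trial.

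**What to change.** - **SAP 9.1:** add two overview rows regardless of relationship, one for TEAEs leading to study drug discontinuation and one for TEAEs leading to study discontinuation. Keep the related-only rows beneath them. Add a listing of AEs leading to study drug discontinuation. If the restriction is intended, declare it in SAP 14 with a reason.
- **SAP 4 and 9.2:** derive the worst post-baseline grade from all valid post-dose results (scheduled, unscheduled and repeat), excluding documented laboratory errors. Keep by-visit tables to scheduled values.
- **SAP 4:** state that safety, PK and as-treated outputs are shown by treatment received.

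The cost is SAP wording, two rows, one listing and a programming flag, with no new data. There is one small drawback: an arm with more unscheduled draws has more chances to show a worse grade, which a footnote to the shift table can point out.
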